**A Prospective, Multi-Center Investigation of the *da Vinci SP*[®]
Surgical System in Colorectal Procedures for Benign and Malignant
Disease**

Protocol Summary

1/31/2023

NCT04403022

**SPONSOR:
Intuitive Surgical, Inc.
[name]
[name]
[contact]
[contact]**

Study #	dV SP – CR-01
Title	A prospective, multi-center investigation of the da Vinci SP [®] Surgical System in colorectal procedures for benign and malignant disease.
Study Design	A prospective, multi-center, single-arm clinical investigation
Study Center	Up to twelve (12) institutions will be included with up to 9 institutions from the United States (US) and up to 3 institutions from South Korea (Appendix II)
Number of Subjects	The study will enroll a maximum of 60 subjects, including 30 subjects who undergo low anterior resection (LAR) with or without total mesorectal excision (TME), and 30 subjects who undergo right colectomy.
Study Objective	To confirm the safety and performance of the da Vinci SP Surgical System, Instruments and Accessories in a complex colorectal procedures such as low anterior resection (LAR) with or without total mesorectal excision (TME). An additional 30 cases of right colectomy will be studied to obtain data on the use of the SP system in a different anatomical location, as suggested by FDA in G20060/S001. Data from these two procedures will be used to support a colorectal indication for the da Vinci SP Surgical System.
Premarket Study Primary Endpoints	
Primary Performance:
 
 The primary performance endpoint will be assessed as the ability to complete the planned da Vinci SP-assisted LAR/TME or right colectomy procedure without conversion to an alternate approach. Conversion to an alternate approach comprises conversion to open, multiport laparoscopic, multiport robotic or hand-assisted approach requiring undocking of the da Vinci SP Surgical System in order to complete the planned procedure using the alternate approach. 
Primary Safety:
 
 The primary safety endpoint will be assessed as the incidence of all intraoperative and post-operative adverse events that occur through the 42-day follow-up period for LAR/TME and right colectomy cases 
Performance and safety endpoints will be analyzed and reported separately for LAR/TME and right colectomy cases

Premarket Study Secondary Endpoint	
For malignant cases:
 
 Rate of positive circumferential resection margin (CRM), rate of positive distal resection margin (DRM), and lymph node yield will be evaluated

Premarket Additional Outcomes of Interest	
 • Operative time (total time to complete the colorectal procedure; including total time using the da Vinci SP Surgical System) • Estimated blood loss (EBL) • Blood transfusions rate • Length of hospital stay (LOS) • Conversion and adverse event rates for right colectomy cases • Mortality rate through 42 days • Unplanned procedure-related readmission rate through 42 days • Unplanned procedure-related reoperation rate through 42 days • Other pathological outcomes for malignant cases • Other anticipated colorectal clinical outcomes to be summarized: 
 ○ Incidence of: anastomotic leak, bowel fistula, perforation, wound infections, use of diverting ileostomy through 42 days ○ Rates of: sexual dysfunction in men, painful intercourse in women through 42 days ○ Bowel recovery outcomes measured as time to: first bowel movement, first flatus, return to clear diet, low residue diet and regular diet • Patient reported outcomes such as International Index Erectile Function (IIEF) and the Abbreviated Sexual Function Questionnaire (ASFQ) are recommended but optional if patient refuses to complete and will be collected preoperatively and at approximately 42-day follow up for LAR/TME cases
Post-Market Long Term Data Collection	
Long-term annual data out to 5 years will be collected from study subjects that underwent LAR/TME or right colectomy for malignant conditions. This data collection will include information on long-term cancer outcomes such as local recurrence, disease free survival, overall survival, any administered adjuvant therapy, and adverse events related to the index procedure. Annual follow-up to assess sexual function via patient reported outcomes using IIEF and ASFQ in LAR/TME cases will also be collected through 5 years.

Study Eligibility Criteria	
Inclusion Criteria:
 
 • Age ≥ 18 years • BMI ≤ 35 • Candidate for single-port robotic-assisted surgery for low anterior resection with or without total mesorectal excision or for right colectomy procedures • ASA ≤ 3 • Willing and able to provide a written informed consent document. • Willing and able to comply with the study protocol requirements including perioperative follow-up examinations at 14 days and 42 days post operatively, and post-market long-term follow-up on an annual basis through 5 years 
Exclusion Criteria:
 
 • Clinical or radiological evidence of distant metastatic disease. Subjects with regional lymph node involvement can be enrolled.

	
 • Life expectancy less than 6 months • Cancer of the anal canal requiring an abdominoperineal resection. • Preoperative colonoscopy demonstrating synchronous colorectal cancer • Subjects with threatened mesorectal margins ($\leq 1\text{mm}$) on MRI or ultrasound (for LAR ONLY) • Subjects with planned major concomitant procedures (eg. hepatectomies, other intestinal resections) or emergent case • Subjects undergoing both LAR/TME and right colectomy during the same operation • History of inflammatory bowel disease • Subject has a known bleeding or clotting disorder • Uncontrolled illness including, but not limited to ongoing or active infection, symptomatic congestive heart failure, unstable angina pectoris, cardiac arrhythmia, or psychiatric illness/social situations that would limit compliance with study requirements • Subject is contraindicated for general anesthesia or surgery • Subject had prior incisional hernia with mesh repair • Subject belongs to vulnerable population • Subject is pregnant or suspected to be pregnant 
Intraoperative Exclusion Criteria
 
 • Subject presents with adhesions or scarring in the pelvis which in the opinion of the investigator limits the ability to perform the minimally invasive procedure
Study Assessments	
Pre Market Assessments:
 
Pre-operative Assessment: Subject demographics, neoadjuvant therapy, diagnostic tests to determine disease status and subject eligibility; patient reported outcomes (IIEF/ASFQ) in LAR/TME cases
 
Intra-Operative Assessments: Assessment of ability to complete surgical procedures (conversion to an alternate approach), total operative time, robotic procedure time, estimated blood loss (EBL), the incidence of blood transfusions, use of diverting ileostomy and intra-operative adverse events
 
Post-Operative (prior to discharge) Assessment: Length of hospital stay, in-hospital mortality, reoperation, bowel recovery outcomes and postoperative adverse events
 
Post-Operative (14 ± 3 days) Assessment: Final pathology outcomes, unplanned procedure-related readmission and reoperation, mortality, postoperative adverse events
 
Post-Operative ($42 \text{ days} \pm 7 \text{ days}$) Assessment: Unplanned procedure-related readmission and reoperation, mortality, postoperative adverse events; patient reported outcomes (IIEF/ASFQ) in LAR/TME cases
 
Post Market Assessments:
 
Annual Assessment through 5-years (± 90 days): local cancer recurrence, disease free survival, overall survival and adjuvant therapy; adverse events

	related to index procedure and patient reported outcomes (IIEF/ASFQ) in LAR/TME cases.
Study Devices	
System: da Vinci SP Surgical System
 
Instruments: The EndoWrist SP Instruments include: a needle driver, medium-large clip applier, monopolar curved scissors, monopolar cautery instrument, fenestrated bipolar forceps, Maryland bipolar forceps, Cadere forceps, round tooth retractor and the Camera Instrument with Firefly imaging system.
 
Accessories: The SP Accessories include: Cannula, Obturator, Entry Guide Kit, Sheaths for Camera and Instruments, tips for Monopolar Curved Scissors, Cautery Hook and Cautery Spatula, Instrument Arm Drape, cautery cords, and SP Access Port Kit.

Sample Size Considerations	The recommended number of evaluable subjects for LAR/TME in this confirmatory study (N=30) reflects the anticipated intraoperative and post-operative adverse event rate based on prior literature of LAR/TME performed by da Vinci Xi Surgical Systems. It is intended to provide a measure by which the performance and safety of the da Vinci SP Surgical System in a clinical setting can be confirmed based on demonstrating equivalence with the da Vinci Xi [®] Surgical System via animal and cadaver testing. An additional 30 cases of right colectomy will be enrolled to obtain data on the use of the SP system in a different anatomical location, as suggested by FDA in G20060/S001. Therefore, a total of N=60 subjects are planned in this confirmatory study.
Data Analysis	All evaluable subjects will be included for analysis regardless of the completeness of their data. Analyses will be based on pre-operative characteristics, intra-operative and post-operative characteristics, and outcomes through 42 days follow-up. Data from both geographies will be reported in aggregates as well as by geography for each procedure.
Study Enrollment & Follow Up	
Enrollment is anticipated to take approximately 18 months.
 
Premarket Assessment: Subjects will be followed postoperatively at 14 days (\pm 3 days) and at 42 days (\pm 7 days).
 
Postmarket Assessment: Subjects with malignant tumors will be followed on an annual basis out to 5 years (\pm 90 days) post-operatively

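### The intraoperative exclusion for pelvic adhesions has no decision point and *evaluable* is undefined, so a conversion could be recorded as an exclusion and the completion rate, mainly for LAR/TME, can be biased upward

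*Combined protocol and SAP*

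**What the plan says.** All references are to the Protocol Summary.

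- **Study Eligibility Criteria, Intraoperative Exclusion Criteria.** A subject is excluded for "adhesions or scarring in the pelvis which in the opinion of the investigator limits the ability to perform the minimally invasive procedure". The criterion gives no time point. It has no label restricting it to LAR, although the mesorectal-margin criterion in the same section has one.
- **Premarket Study Primary Endpoints, performance.** Success is the ability to complete the planned SP-assisted "LAR/TME or right colectomy procedure without conversion to an alternate approach". The section adds: "Conversion to an alternate approach comprises conversion to open, multiport laparoscopic, multiport robotic or hand-assisted approach requiring undocking of the" SP system.
- **Premarket Study Primary Endpoints, safety.** Adverse events during and after surgery are counted to day 42 for LAR/TME and right colectomy cases. Both endpoints are reported separately by procedure.
- **Data Analysis.** "All evaluable subjects will be included for analysis regardless of the completeness of their data". *Evaluable* is not defined there or elsewhere.
- **Sample Size Considerations and Number of Subjects.** The first plans 30 evaluable LAR/TME subjects. The second caps enrolment at 60, including 30 who undergo LAR.

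The document does not say whether an intraoperatively excluded subject counts as a conversion, is replaced, is followed for adverse events, or is reported at all.

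**The concern.** The endpoint asks whether the planned procedure could be completed. The exclusion removes subjects in whom, in the operating investigator's opinion, the ability to perform it is limited. Take a subject in whom the SP system is docked, pelvic adhesions are found, and the operation is finished by another approach. That subject fits the definition of conversion and can also fit the exclusion, and nothing says which label prevails. One label is a failure on the primary endpoint; the other can take the subject out of the analysis.

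The choice is made by an investigator who already knows how the operation is going. The study has a single arm, so no control group is subject to the same rule. With 30 subjects per procedure, one relabelled failure moves the completion rate by about 3 percentage points. The safety endpoint has the same gap, because an injury in an excluded subject has no guaranteed place in the count. The results are intended to support a colorectal indication.

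**Working it through.** **The plan's own figures.** The total of 60 is 30 + 30, which agrees. The 30 for LAR/TME cannot be reproduced: no adverse event rate, performance goal, error rate, power or precision target is given.

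**Inputs.** n = 30 LAR/TME subjects is from the document. The number excluded during surgery (k) and the number of counted conversions (c) are assumptions, because the document gives neither. Intervals are exact (Clopper-Pearson) 95%.

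**Two readings of n = 30.**

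- Not replaced: 30 are started and exclusions shrink the denominator. Reported conversion rate = c/(30 − k). With all started subjects kept and exclusions counted as failures, it is (c + k)/30.
- Replaced: recruitment continues until 30 are evaluable. Reported conversion rate = c/30. With all started subjects kept, it is (c + k)/(30 + k).

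**Illustration, k = 3 and c = 1.**

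| Reading | Reported conversion | All started, exclusions as failures | Gap |
|---|---|---|---|
| Not replaced | 1/27 = 3.7% (0.1 to 19.0%) | 4/30 = 13.3% (3.8 to 30.7%) | 9.6 points |
| Replaced | 1/30 = 3.3% (0.1 to 17.2%) | 4/33 = 12.1% (3.4 to 28.2%) | 8.8 points |

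**Range.** The gap in completion rate, for c = 0 to 3 with replacement and c = 0 to 2 without:

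| k | Gap (percentage points) |
|---|---|
| 0 | 0 |
| 1 | 2.9 to 3.3 |
| 2 | 5.6 to 6.7 |
| 3 | 8.2 to 10.0 |
| 5 | 12.9 to 16.7 |

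**Effect on the lower limit.** With replacement, c = 0 and k = 3, the reported result is 30/30 = 100% (lower limit 88.4%). Over all started subjects it is 30/33 = 90.9% (lower limit 75.7%).

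**When there is no upward bias.** If c = 2, k = 2 and both excluded subjects would have completed, the reported 28/30 = 93.3% compares with 30/32 = 93.8%. The reported rate is then slightly low. Treating every exclusion as a failure therefore gives the largest possible gap for a given k.

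**The case against.** The strongest reply is that the criterion is an ordinary screen. It sits under eligibility, and its wording suits a finding at first inspection. Conversion requires undocking, so an exclusion made before docking cannot be a conversion. This stands for pre-docking exclusions, but the document does not limit the criterion to them.

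A second reply is that the criterion refers to the minimally invasive procedure in general, not to SP. A subject who could still be operated on by multiport laparoscopy or a multiport robot would then not be excludable, and that switch would remain a conversion. This narrows the overlap but does not remove it: a post-docking switch to open surgery for pelvic adhesions still fits both definitions. Conversions for any other reason count in any case.

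A reader might infer more than the document supports:

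- *That the rate is biased.* It can be. The number of exclusions is unknown, and the document lists no causes of conversion; the link to adhesions is inferred from the criterion's wording.
- *That the plan's denominator would be 27.* Replacement to 30 evaluable subjects is an equally open reading.
- *That adverse events in excluded subjects are dropped.* The endpoint covers all events in the cases, and Study Assessments collects intraoperative events. Whether an excluded subject is a case is simply not stated.
- *That only LAR/TME is affected.* The criterion carries no such label; the pelvic site makes LAR/TME the procedure mainly affected.
- *That a comparison with published Xi rates would favour SP.* No such comparison is specified. The Xi literature is cited for the anticipated adverse event rate behind the sample size, and equivalence is attributed to animal and cadaver testing.

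Finally, this is a summary, and a fuller plan may contain the missing rules. If so, the sponsor need only point to them.

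**Conclusion.** The concern holds as a possibility that the written rules allow. An investigator-judged exclusion without a decision point, combined with an undefined analysis population, lets a post-docking conversion for pelvic adhesions be classified as an exclusion. The clause about completeness of data does not close the gap: it keeps evaluable subjects with missing data and does not bring excluded subjects back.

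Each failure relabelled in this way raises the reported LAR/TME completion rate by about 3 points. The illustrative gap of roughly 9 to 10 points rests on the assumed counts and on every excluded subject being a failure. No performance goal is stated, so there is no pass or fail decision that the bias could be shown to reverse. This is a cheap improvement to the plan, not evidence that its results would be wrong.

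**What to change.** 1. State that, for the analysis, the intraoperative exclusion applies only when it is decided and documented before the SP system is docked, and that a switch to another approach after docking counts as a conversion.
2. Define *evaluable* to match, and say whether excluded subjects are replaced.
3. Report as a sensitivity analysis the completion rate over all subjects with a skin incision for the study procedure, with intraoperative exclusions counted as not completed. Label it as a different quantity from one minus the conversion rate, because pre-docking exclusions are not conversions.
4. Count adverse events through day 42 for all these subjects.
5. List every intraoperative exclusion with its reason and timing, by procedure.

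These changes concern classification and reporting only; the surgeon's choice of approach is untouched. The cost is a few sentences, one analysis line and a listing. Excluded subjects must be followed to day 42, and the reported completion rate may look slightly less favourable.
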